4.10.2. Time to Negative PCR

Negative PCR is defined as a quantitative PCR result below the lower limit of detection.

Time to negative polymerase chain reaction (PCR) will be defined as the number of days from baseline positive PCR (Day 0) to the first of 2 consecutive negative PCR results.

- If only the final collected PCR is negative, this will be the date of negative PCR.
- If the final collected result is positive, the participant will be assumed censored without negative PCR

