- SARS-CoV-2 diagnostic test result
 - Diagnostic testing must be an approved molecular or antigen diagnostic test for SARS-CoV-2 from any upper respiratory specimen performed at screening or enrollment or within 5 days of enrollment. The test used must be authorized for use by the relevant national authority for the detection of SARS-CoV-2 in the country where the test is administered. Historical testing results will be acceptable if testing performed within the required window. The test result must be available and reviewed by site PI or study staff to confirm eligibility.

C 9.2.5 Blood Volumes

The maximum volume of blood drawn at any one visit will not exceed 30 mL.

C 9.2.6 Pharmacokinetics

Plasma samples for PK evaluation will be collected at Day 0, Day 3, and Day 14. The analysis will include levels of upamostat and its active metabolite, WXUK1, for each of these time points.

Day 0: all patients will have a specimen drawn prior to first treatment with study medication.

Patients will be randomized to one of two sampling regimens for Day 3:

A) Day 3 specimen within 2 hours prior to dosing;

OR

B) Day 3 specimen 2-4 hours after dosing.

Day 14: all patients will have a specimen drawn 22-26 hours after previous dose.

An attempt will be made to get a specimen 22-26 hours after the last dose from patients who stop treatment early.

C 9.4 Study Visits

Study Visits will be conducted according to the Master Protocol with the following additions and exceptions as presented in [Section 1.2 Schedule of Activities](#).

Activities in the Master Protocol that do not apply to participants randomized to the upamostat Appendix C are indicated by ~~strikethrough~~, while activities that have been added are indicated by **bold** text.

C 9.4.1 Screening Visit – In Person or Remote (Within 24 hours Prior to Enrollment)

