- Concomitant medication Review
- Daily Symptom Follow Up Questionnaire (daily until Day 28 then at **Weeks 8** and 12)
- Upper respiratory specimen collection
- Clinical outcome assessment
- Vital signs
- Physical exam
- **Pregnancy test**
- Venous blood sampling
 - Hematology
 - Chemistry
 - **Coagulation studies**
 - **Whole blood, plasma, and serum storage for possible future research**
- Adverse Event Recording and Reporting

C 9.4.8 Week 8 Visit – In Person

This visit is scheduled to take place In Person at Week 8. Every effort should be made to complete the Week 8 visit requirements at Week 8; however, the visit may take place — if necessary +/- 1 week.

- Concomitant medication review
- Daily Symptom Follow Up Questionnaire (daily until Day 28 then at **Weeks 8** and 12)
- Upper respiratory specimen collection
- Clinical outcome assessment
- Vital signs
- Physical exam
- Venous blood sampling
 - Hematology
 - Chemistry
 - **Coagulation Studies**
 - **Anti-SARS-CoV-2 IgM and IgG**
 - **Whole blood, plasma, and serum storage for possible future research**
- Adverse event recording and reporting

C 9.4.9 Week 12 ~~In Person OR Remote~~

This visit is scheduled to take place Remotely at Week 12. Every effort should be made to complete the Week 12 visit requirements at Week 12; however, the visit may take place — if necessary +/- 2 weeks.

- ~~SARS-CoV-2 vaccination status~~
- Concomitant medication review
- Daily Symptom Follow Up Questionnaire (daily until Day 28 then at **Weeks 8** and 12)
- Upper respiratory specimen collection (self-collection)
- Clinical outcome assessment
- Adverse Event Recording and Reporting

C 9.4.10 Unscheduled Visits – In Person or Remote

An unscheduled visit is defined as any visit to the clinical trial site outside of the protocol evaluation time points, where the participant is seen by a member of the clinical research staff. Participants will be encouraged to report any medical problems or discomfort to the study staff and may be instructed to return to the clinical trial site if they experience new or worsening COVID-19 symptoms or become infected with SARS-CoV-2 any time after enrollment. Remote visits may include visits by the study staff to the participant or via phone/video conference. If remote visit not feasible or is not permissible under local rules or standards, the visit may be conducted in person.

In the event of an unscheduled visit these procedures may be done according to clinical judgement:

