4.10.1. Resolution of Symptoms

The primary analyses will be based on an intent-to-treat approach. Therefore, every patient in the mITT Population will be analyzed. A single imputation approach for each patient with missing data will be utilized with a range of sensitivity analyses exploring the sensitivity of the results to the missing data.

A single imputation approach will be conducted for the primary analysis for each patient with missing daily observations. The following single imputation will be utilized:

- If the patient's last day was symptom free, then the patient will be assumed symptom free, and their time of resolution will be the first symptom free day.
- If the patient's last day was symptoms alleviated, then the patient will be assumed symptom alleviated and their time of alleviation the first day of alleviated symptoms.
- If the patient's last day was non-alleviated or resolved symptoms, they will be assumed censored without alleviation or resolution at the last observed day.

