5.2.3. Secondary Outcomes: Virological

- Comparison of active and placebo treatment groups in time to negative RT-PCR
 - Timeframe: Day 0 to Week 12
 - Time to negative RT-PCR will be defined as the time of the first of two consecutive readings below the lower limit of detection. A Cox proportional hazards model will be used to analyze the time to negative PCR.
 - A Kaplan-Meier curve of time to negative PCR will be presented.

Analysis population: The mITT population will be used for secondary endpoint analyses and will be repeated with the Per Protocol Population and the Baseline COVID-19 PCR Positive Population.

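### SAP 4.10.2: the final-positive PCR rule lacks the condition that no confirmed negative pair exists, gives no censoring date, and sits beside an ambiguous final-negative rule (minor, one secondary endpoint)

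*SAP*

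**What the plan says.** SAP 4.10.2 defines a negative as a quantitative result below the detection limit and measures the endpoint as the "number of days from baseline positive PCR (Day 0) to the first of 2 consecutive negative PCR results". SAP 5.2.3 repeats the definition: "Time to negative RT-PCR will be defined as the time of the first of two consecutive readings below the lower limit of detection". Protocol C 13.5.1.2 (Secondary Outcome: Virological) uses the same definition. None of the three makes an exception for a positive after the pair.

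Two handling rules follow in SAP 4.10.2:

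- Final negative: "If only the final collected PCR is negative, this will be the date of negative PCR".
- Final positive: "If the final collected result is positive, the participant will be assumed censored without negative PCR".

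Neither is expressly limited to participants without a confirmed pair, and the second names no date. By contrast, the corresponding rule for symptoms in SAP 4.10.1 says that "they will be assumed censored without alleviation or resolution at the last observed day".

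The protocol's Schedule of Activities plans seven post-baseline swabs: Days 3, 7, 10, 14 and 28, and Weeks 8 and 12. Swabs may also be taken at unscheduled visits, and C 9.4.10 says participants may be told to "return to the clinical trial site if they experience new or worsening COVID-19 symptoms". The analysis is a Cox model in the mITT population, repeated in the Per Protocol and Baseline COVID-19 PCR Positive populations.

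**The concern.** A participant with the sequence positive, negative, negative, positive has an event under the definition and is censored under the final-positive rule. Two programmers could each follow SAP 4.10.2 and build different event sets. The sequence can arise, because swabbing continues to Week 12, long after many participants may have cleared.

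Two smaller gaps sit alongside. A censored participant has no stated censoring date. And if *only* in the final-negative rule means that the last swab is the sole negative, then positive, negative, positive, negative falls under no rule.

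Time to negative PCR is the only endpoint for the virologic objective. The repeats in the other two populations do not settle these questions, because the same derivation is used there. Choosing between readings after unblinding would be a data-dependent choice.

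**Working it through.** The documents give no figure for this rule, so there is none to reproduce. Two checks are possible.

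**1. Which sequences the rules classify**

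Input: seven planned post-baseline swabs, baseline positive, none missing, giving 2^7 = 128 possible sequences.

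The number of sequences of length n with no two adjacent negatives follows a(n) = a(n−1) + a(n−2), with a(1) = 2 and a(2) = 3. This gives a(6) = 21 and a(7) = 34.

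- Sequences containing a pair: 128 − 34 = 94.
- Ending positive: 64. Without a pair: a(6) = 21. With a pair: 64 − 21 = 43.
- Ending negative: 64. Without a pair: 34 − 21 = 13, of which 1 has the last swab as its sole negative and 12 have an earlier isolated negative. With a pair: 64 − 13 = 51.

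If the final-positive rule is applied literally and *only* is read strictly, the result is 51 + 1 = 52 events, 64 censored and 12 unclassified. If the rules are fallbacks and any unconfirmed final negative counts, it is 94 + 13 = 107 events and 21 censored. These are counts of possible strings, not frequencies. They show where the text allows two answers, not how often that will occur.

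**2. What the literal reading would do to the hazard ratio**

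All inputs except the visit days are assumptions: control median clearance of 7, 10 or 14 days; true hazard ratio 1.5; clearance first seen at the next planned swab; and equal rates in both arms of a positive Week 12 swab after a pair completed by Week 8. The literal rule is taken to censor at Day 84. Cox model with Efron ties, 200,000 simulated participants per arm; ranges are across the three medians.

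| Assumed clearance | 0% late positive | 2% | 5% | 10% |
|---|---|---|---|---|
| Exponential | 1.46 | 1.35–1.38 | 1.30–1.32 | 1.23–1.24 |
| Weibull, shape 0.75 | 1.48 | 1.38–1.44 | 1.32–1.38 | 1.24–1.30 |
| Weibull, shape 1.5 | 1.43–1.44 | 1.33–1.36 | 1.27–1.29 | 1.20–1.25 |
| Exponential, 10% never clear | 1.24–1.26 | 1.22–1.24 | 1.20–1.21 | 1.16–1.18 |

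The 0% column equals the fallback reading. Its distance from 1.5 comes from the visit grid and, in the last row, from persistent positives, not from this rule. The rule's effect is the movement across a row. With a true hazard ratio of 1, equal late-positive rates and no persistent positives, every result lies between 0.99 and 1.01.

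**The case against.** The fallback reading is the natural one. The final-negative rule makes sense only where there is no pair, and the final-positive rule is its companion. Its outcome, being censored without a negative PCR, does not describe someone with a confirmed pair. The section belongs to the missing-data conventions and follows symptom rules that also act on the last observation. This stands: a reader might infer that the SAP builds a bias into the virologic estimate, and the documents do not support that. They support only that the text permits a biased derivation.

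A reader might also take 43 of 64 as a rate of misclassification. It is not one, since many of those strings need several reversals between positive and negative. Likewise, the 12 sequences are not plainly uncovered. If *only* means that the final negative is unconfirmed, they are covered. The wording is ambiguous rather than demonstrably incomplete.

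The simulated shifts are modest beside sampling error. With 150 events (an assumed figure, matching the participant count for the interim trigger in protocol C 13.6) and equal arms, the 95% interval extends by a factor of exp(1.96 × √(4/150)) = 1.38 either way. At a 5% late-positive rate with exponential clearance the shift is at most 1.46/1.30 = 1.12. The last PCR date is also the obvious censoring date. These points limit the severity, but they do not make the text say what is probably meant.

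Finally, a reader might infer that the main population is wrong. Entry is allowed on an antigen test, or on a test "performed at screening or enrollment or within 5 days of enrollment", so mITT can include participants without a positive baseline PCR, who have no defined time origin. But nothing in the SAP says they count as Day 0 events, and the planned Baseline COVID-19 PCR Positive analysis covers the issue. No change of main population is called for.

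**Conclusion.** The point holds as a drafting fault of minor severity. Taken literally, the final-positive rule contradicts the endpoint definition in SAP 4.10.2, SAP 5.2.3 and protocol C 13.5.1.2. It states no censoring date, and the final-negative rule is ambiguous after an earlier isolated negative.

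The size depends on the reading. As a fallback, there is no bias. Taken literally, with a working drug and equal late-positive rates, the hazard ratio moves toward 1 by an amount set by a rate that the documents do not give, and by less if some participants never clear. With no true effect and equal rates there is no bias, so this is not a route to a false positive. One secondary endpoint is affected; the primary analysis and the stated power are not.

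**What to change.** In SAP 4.10.2:

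1. State that the first of two consecutive negatives fixes the event date, whatever later swabs show.
2. Apply both handling rules only when no such pair exists.
3. In that case, count a final negative as the event on its own date, even if an isolated negative came earlier.
4. In that case, censor a final positive at the date of the last PCR.
5. Report by arm the number of participants with a positive PCR after a confirmed pair.
6. Note that mITT participants without a positive baseline PCR have no defined time origin, and that the planned Baseline COVID-19 PCR Positive analysis addresses this.

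The cost is a few sentences and one count by arm, recorded in SAP Appendix A if made before unblinding and in the CSR if later. No new data are needed. The one drawback is that a late positive no longer affects the event, which is why item 5 reports it separately.

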5. STATISTICAL ANALYSES

5.1. Description of participant population

5.1.1. Disposition

The number of subjects screened and in each study population will be tabulated by treatment group. Similarly, number of subjects in each study population will be tabulated additionally by country.

The subjects' final status, including number and percentage of subjects who complete the study, are lost to follow-up, or terminate early along with primary reason for discontinuation and reason for treatment discontinuation based on Case Report Form (CRF) will be tabulated using the Safety Population and by treatment group.

5.1.2. Protocol Deviations

The frequency of protocol deviations will be summarized with frequency tabulations by treatment group and major/minor classification using the Safety Population. Furthermore, all protocol deviations will be listed individually, including major/minor classification.

5.1.3. Study Intervention Compliance

Treatment compliance (percentage of planned doses received) will be calculated as

- Participant- Reported Compliance: (number of participant-reported doses via diary / expected doses x 100%)
- Observed Compliance: (30 minus number of pills returned / expected number of pills taken x100%)

summarized by treatment group for the Safety Population. Dosing details will be provided in listings.

5.1.4. Demographics and Baseline Characteristics

Baseline demographic and baseline characteristics information (age, sex, height, weight, BMI, race) will be summarized by treatment group for the Safety Population. Results will also be stratified by country.

5.1.5. Medical History

Medical history data, including prior procedures and therapies, will be summarized for the Safety Population by treatment group using frequency tabulations by the Medical Dictionary for Regulatory Activities (MedDRA, version 24.0 or higher) system organ class and preferred term.

5.1.6. Concomitant Therapy

Patient-reported medication history during the 30 days prior to ICF signing will be recorded at Screening. Thereafter, any changes in concomitant medications or new medications added will be recorded in the data collection forms.

While most systemic medications taken by the subject, other than study drug, are considered concomitant medications and should be recorded, the following specific exceptions do not need to be recorded: topical medications (eye drops, ear drops, intranasal drops or sprays, dermatologic treatments, topical lidocaine).

In contrast, the following should be recorded: vitamins and supplements (e.g., vitamins, minerals, herbal supplements, dietary supplements, iron/ferrous sulfate, magnesium, calcium, electrolyte replacements) and nicotine replacement products (e.g., patches, lozenges, gums, nasal sprays).

Concomitant medications will be coded using the WHO Drug (version WHO_DDE_B3_sep2020 or higher) and summarized by treatment group for the Safety Population. A separate summary of concomitant medications considered rescue medications (i.e. those taken for COVID-19 symptoms) will be provided.

By-participant listings will accompany the tables.

5.2. Efficacy Assessments

The key efficacy assessment in the early treatment indication is time to sustained alleviation or resolution of symptoms among patients who were SARS-CoV-2 positive on initial screening at a local laboratory, either by PCR or rapid antigen test. Time to sustained alleviation or resolution of targeted COVID-19 symptoms will be defined as the number of days from randomization in a PSA (Step 2 of randomization) to the first day the participant reports all symptoms as mild or none (≤ 1 on the Daily Follow Up Symptom Questionnaire), or no worse than the usual severity, for at least 3 consecutive days (the first day being considered the Event Day).

Targeted symptoms include stuffy or runny nose, hoarse voice, sore throat, difficulty breathing, cough, fatigue, muscle or body aches, headache, chills or shivering, feeling hot or feverish, nausea, vomiting, diarrhea, loss of taste, loss of smell. The Symptom Severity Score is collected in the Symptom Follow Up Questionnaire as the Overall Symptom Severity. Overall Symptom Severity may be rated none (0), mild (1), moderate (2), or severe (3). Loss of taste and loss of smell may be rated as the same as usual (0), less than usual (1), or no sense of taste/smell (2, considered a “severe” rating).

The general statistical approach will compare outcomes among participants randomized to receive the active agent, upamostat, to outcomes among participants who were eligible to have been randomized to upamostat but who were randomized instead to any of the placebo arms enrolling at that time. This ensures that the comparison is limited to concurrently randomized participants eligible to receive upamostat.

Unless otherwise specified, for each analysis, a 5% two-sided significance will be used. 95% confidence intervals will be presented to summarize each effect estimate. Dichotomous outcomes will be summarized with relative proportions. Ordinal outcomes will be summarized with stacked bar plots, cumulative proportion graphs, and percentiles. Kaplan-Meier plots will be used for summarizing time to event outcomes. Continuous measures will be summarized with box plots (means, medians, and inter-quartile ranges).

Sustained alleviation or resolution will be defined as the number of days from randomization within a PSA to the first day the participant reports all symptoms as mild or none (≤ 1 or returning to pre-illness levels) for at least 3 consecutive days (the first day being considered the Event Day). Targeted symptoms will be used for analysis (Supplement 3). Symptoms will be collected at Enrollment using the Screening Symptom Questionnaire to establish baseline symptom status.

5.2.1. Primary Outcome

- Time to sustained alleviation or resolution of COVID-19 symptoms evaluated from Day 0 through Day 28 assessed via completion of a Daily Follow Up Symptom Questionnaire
 - Analysis population: mITT

The primary objective is to estimate the relative time to sustained alleviation or resolution of symptomatic COVID-19 infection for a participant that receives upamostat compared to a participant that does not receive upamostat.

The primary analysis population is the Modified Intent-to-Treat Population.

The estimand of interest is the hazard ratio of a participant that has symptomatic COVID-19 with standard of care background therapy when starting treatment with upamostat compared to no upamostat. A hazard ratio greater than 1 indicates a shorter time to resolution of symptomatic COVID-19 infection

The primary analysis model is a Cox proportional hazards model for the time to alleviation or resolution of COVID-19 symptoms, with treatment arm (active upamostat vs placebo) as a fixed

covariate with proportional effect. The model estimated hazard ratio will be used as the estimator for the estimand of interest. The estimate and 95% confidence interval for the hazard ratio will be presented.

The primary hypothesis test is that upamostat increases the hazard (decreases time to resolution) of COVID-19 symptoms. A hypothesis test will be conducted for testing whether the upamostat hazard ratio is greater than 1 at a one-sided 2.5% level.

Additional sensitivity analyses for the primary analysis will utilize additional covariate adjustments in the Cox proportional hazards model. The analysis will be repeated for the Per Protocol Population and the Baseline COVID-19 PCR Positive Population.

